### **3.5 End-of-Study (EOS) Phase (Visit 9, Week 16, Days 112±4)/Early Termination**

The EOS Visit (Visit 9) will be conducted 4 weeks following the last scheduled treatment Visit. Subjects will report to the clinic in the morning following a 10-hour fast. The following procedures will be performed:

- Review of concomitant medication;
- Complete PE, only if the investigator deems it necessary;
- Measurement of weight;
- Collection of unused ORMD-0801 medication;
- 12-Lead ECG, only if the investigator deems it necessary;
- Measurement of vital signs (SBP/DBP, heart rate and oral temperature), only if the investigator deems it necessary;
- Fasted blood samples will be collected for clinical laboratory evaluations (see [Section 6.5.5.1](#) for a complete list of tests performed):
  - Serum Chemistry including liver function tests (LFTs) and blood lipids;
  - Hematology;
- Measurement of fasting blood glucose and fasting insulin for HOMA estimates;
- Review/Collect subject diaries for self-monitored fasting morning blood glucose;
- HbA1c;
- Adiponectin test;
- AEs/SAEs assessment.

Patients who are discontinued early from the study will complete the EOS evaluations at the time of early discontinuation.

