### **3.7 Self-Monitoring Fasting Blood Glucose and Patient Diaries**

All patients will self-monitor fasting morning blood glucose levels three (3) times weekly during the run-in and treatment period. Monitoring must be performed at the same time each designated day ( $\pm$  10 minutes) prior any caloric intake. Patients will be required to record the values in a patient diary and bring the diary to each clinic visit. Information recorded for the fasting blood glucose will be reviewed by the clinical research coordinator for completeness and transcribed onto electronic case report form (eCRF). During the study, both fasting finger stick glucose and laboratory fasting plasma glucose will be obtained.

If a fasting blood glucose measures greater than or equal to 270 mg/dL (15 mmol/L) during daily self-monitoring or during any in-clinic visit, the patient will be required to contact the clinic to report the value. The patient may be required to return for an unscheduled visit to the clinic for a repeat measurement of fasting blood glucose within one week after the original measurement. If

the patient is invited for an unscheduled visit, blood will be drawn and sent to lab for plasma glucose determination. If the repeat measurement is also greater than or equal to 270 mg/dL, the patient will be discontinued from treatment with study drug and offered rescue medication. The patient will continue to be seen for all remaining study visits, if possible.

If a fasting blood glucose value is <70 mg/dL, the patient should drink 1 cup of orange juice or swallow 3-4 glucose tablets. The patient must check his blood sugar after 10 min and if the blood glucose level does not raise, the patient needs to drink another cup of orange juice or swallow 3-4 glucose tablets. Blood sugar must be checked again after 10 minutes. The patient must call to report this event to the study site and record all blood glucose levels in the diary.

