-  Screening labs will include standard hematology, fasting serum chemistry, plus TSH. FSH will also be performed for women who are post-menopausal, if results are not available.
-  Adverse events will be collected throughout the study beginning from the time the patient signs the consent form until the EOS (Visit 9) evaluations.

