## 6.6 Review and Documentation of Medications and Supplements

All medications or supplements subjects are taking or have taken within 30 days prior to Visit 1 through Visit 9 will be recorded in the subject's medical record and the eCRF.

All medications and supplements (other than IMP) taken by the subject after Visit 1 through Visit 8 assessments will be considered "concomitant" medications and supplements.

Medications and supplements taken prior to Visit 1 that are no longer being taken at Visit 1 will be considered "prior" medications and supplements.

Medications and supplements should be recorded according to the generic name when possible. The use of concomitant medications and supplements should be limited to those that are medically necessary. Any medication or supplement used should have an indication recorded, and for concomitant medications and supplements, this indication must be represented as either for the treatment of an AE, for the management of a pre-existing condition, or for prophylaxis.

Dosage increases for any concomitant medication or supplement should be noted and the reason for the dosage increase recorded as an AE (assumes worsening condition). The side effects of concomitant medications will be recorded as AEs.

Any subject whose condition becomes disqualifying during the course of the study may be treated for that condition. If the condition is suspected during Screening, the subject should not be enrolled. Treatment of the condition should be instituted according to the Investigator's/attending physician's judgment.

Medications that have no treatment intent but rather are part of supportive routine care such as local anesthetics, intravenous solutions to maintain fluid balance and keep access open, medications used for prophylaxis, and narcotics for postsurgical pain must also be recorded in the subject's medical record and eCRF.

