### 8.2 Safety Evaluation

#### 8.2.1 Adverse Events

AEs will be coded using the most current version of MedDRA. The severity of AEs will be graded according to NCI CTCAE version 4.03. AEs will be regarded as “pretreatment” if they occur during the Placebo Run-in Phase. TEAEs are defined as any AE that starts or increases in severity after the first dose of IMP at Visit 3.

The incidence of TEAEs will be tabulated by MedDRA preferred term, system organ class, treatment group, severity, and assigned relationship to IMP. The incidence for each TEAE will be provided as the total number of subjects that experienced the TEAE, as well as the percentage of the population that this represents. If a TEAE is reported more than once for a given subject, the greatest severity and the worst-case attribution will be presented in the summary tables.

TEAEs will be listed for individual subjects, along with information regarding onset and end dates, onset time where available, severity, seriousness, relationship to IMP, action taken, and outcome. A similar listing will be prepared for the pretreatment AEs.

Pretreatment AEs and TEAEs that lead to withdrawal from the study will be separately listed and summarized. Similarly, separate tabulations and listings will be prepared for pretreatment and treatment emergent SAEs.

Descriptive statistics will be generated as appropriate (i.e., frequency for categorical data). Inferential statistical analysis comparing the AE data between Active treatment and Placebo is not planned.

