### 8.2.3 Vital Signs

Individual vital sign measurements (seated SBP/DBP, heart rate and oral temperature) will be listed by measurement time and summarized using descriptive statistics as appropriate (i.e., mean, median, range, and standard deviation). Individual change from baseline (screening) in vital sign measurements will be calculated and summarized descriptively. A clinically significant change from baseline will be recorded as a TEAE if deemed appropriate by the Investigator.

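### The TEAE window in Section 8.2.1 has no end tied to last dose, so events after study drug stops or after rescue are pooled with on-drug events in the arm comparison

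*Combined protocol and SAP*

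**What the plan says.** - **Window.** Section 8.2.1: "TEAEs are defined as any AE that starts or increases in severity after the first dose of IMP at Visit 3". Events in the placebo run-in are classed as pretreatment. No end is given.
- **Collection.** Table 1, footnote 13: "Adverse events will be collected throughout the study beginning from the time the patient signs the consent form until the EOS (Visit 9) evaluations". Section 3.5: "The EOS Visit (Visit 9) will be conducted 4 weeks following the last scheduled treatment Visit".
- **Stopping and rescue.** Section 3.7: after a repeat high fasting glucose, "the patient will be discontinued from treatment with study drug and offered rescue medication". Then: "The patient will continue to be seen for all remaining study visits, if possible". Patients stopped for repeated low values also remain in the visit schedule.
- **What counts.** Section 6.6: "The side effects of concomitant medications will be recorded as AEs". Section 7.5 makes hypoglycaemic events AEs, and Section 7.3.1 lists hypoglycaemia as an event of special interest.
- **Display.** Section 8.2.1 tabulates TEAEs as subject counts and percentages by arm, severity and causality, with dated listings. It plans no test between arms. Section 2.3 makes safety the primary endpoint.
- **Vital signs.** Section 8.2.3, where baseline is Screening: "A clinically significant change from baseline will be recorded as a TEAE if deemed appropriate by the Investigator". The parallel sentences for laboratory values (8.2.2) and physical examination (8.2.5) say AE, not TEAE.

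**The concern.** The table that carries the primary endpoint mixes three states: on study drug, off study drug, and off study drug but on another glucose-lowering treatment. A patient stopped for high glucose who later becomes hypoglycaemic on the rescue drug adds a case to the arm originally assigned. Nothing in Section 8.2 separates that case from one that arose while capsules were being taken.

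If the study drug lowers glucose, rescue may be more frequent on placebo, and such cases would then narrow the contrast. If patients in the active arm are stopped or rescued more often, the same rule widens it. Because no test is planned, readers will compare raw percentages based on about 24 and 12 subjects, where single cases matter.

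The 8.2.3 wording is a separate fault at the other end of the window. It can label as treatment-emergent a change that was present before any randomized dose.

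**Working it through.** The plan states no rate or power figure to reproduce. The checks below use its visit days and sample size. All event and rescue rates are assumptions.

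**1. Length of the off-drug window** (Table 1: Visit 8 at Day 84±4, Visit 9 at Day 112±4)
- Completer: (112 − 84)/112 = 28/112 = 25%. Visit windows allow 108 − 88 = 20 to 116 − 80 = 36 days.
- Study drug stopped at Day 28, stays to Visit 9: (112 − 28)/112 = 84/112 = 75%.
- Stopped at Day 56: 56/112 = 50%.

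Subjects who leave the study altogether have the Visit 9 evaluations at that point (Section 3.5), so they have little or no off-drug window.

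**2. Weight of one subject** (Section 5.2: about 36 at 2:1, so 24 active and 12 placebo)
- Placebo 1/12 = 8.3 points; active 1/24 = 4.2 points.
- Assumed on-drug result 6/24 vs 1/12: 25.0 − 8.3 = 16.7 points.
- One post-rescue placebo case: 25.0 − 16.7 = 8.3 points. Two: 25.0 − 25.0 = 0.
- Two post-drug active cases instead: 8/24 − 1/12 = 33.3 − 8.3 = 25.0 points.

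**3. Follow-up alone** (assumed 12-week incidence 25% active, 8% placebo; placebo background rate continues in both arms for 28 days)
- Added risk: 1 − (1 − 0.08)^(28/84) = 0.027.
- Active: 1 − 0.75 × 0.973 = 0.271. Placebo: 1 − 0.92 × 0.973 = 0.105.
- Difference 16.5 points against 17.0 on drug; risk ratio 2.6 against 3.1.
- With 20% vs 5% and 30% vs 10% as alternatives, the loss is never more than 0.7 points.

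**4. Adding rescue** (same base; rescue in a fraction r of placebo and none of active; hypoglycaemia risk h after rescue)

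Placebo = 1 − (1 − 0.105)(1 − r·h). The last column is the exact binomial probability that the observed active rate does not exceed placebo, with Bin(24) and Bin(12).

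| Case | Active | Placebo | Difference (points) | P(active ≤ placebo) |
|---|---|---|---|---|
| On-drug only | 0.250 | 0.080 | 17.0 | 10% |
| Follow-up only | 0.271 | 0.105 | 16.5 | 13% |
| r = 0.10, h = 0.3 | 0.271 | 0.132 | 13.8 | 19% |
| r = 0.25, h = 0.3 | 0.271 | 0.172 | 9.8 | 29% |
| r = 0.40, h = 0.3 | 0.271 | 0.213 | 5.8 | 39% |

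- Over r = 0.10 to 0.40 and h = 0.1 to 0.6, the difference runs from 15.6 to −4.9 points.
- Cancellation in expectation needs r·h = 1 − (1 − 0.271)/(1 − 0.105) ≈ 0.185, for example 40% rescued with a 46% risk.

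**5. A second set of assumptions** (on-drug 15% vs 3%; active rescue = placebo rescue/2.5)
- At 25% placebo rescue, 10% active rescue and h = 0.3: placebo 1 − 0.97 × 0.925 = 10.3%; active 1 − 0.85 × 0.97 = 17.5%. The difference is 7.3 points against 12.
- Over r = 0.10 to 0.40 and h = 0.1 to 0.5, it runs from 11.4 to −0.6 points.

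**6. Timing in 8.2.3.** Table 1 schedules vital signs at Visits 2 and 3. Section 6.5.2 puts them before any blood draw at the same time point, and Table 1 footnote 5 puts blood samples before in-clinic dosing. A Visit 3 reading therefore precedes the first randomized dose, and a Visit 2 reading falls in screening or run-in. Neither meets the start rule in 8.2.1, yet 8.2.3 as written calls a significant change from Screening a TEAE at any visit.

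**The case against.** The strongest reply is that the plan already has a partial safeguard. TEAEs are also tabulated by causality, and Section 7.6 makes concomitant drugs a ground for an Unlikely rating. Listings carry onset dates and action taken, and concomitant medications are listed. In a study of 36, a rescue-related event can be traced. That stands, but it rests on the investigator's causality rating and on separation after the fact, not on a stated rule.

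Several other points also stand:
- Completers have the same off-drug follow-up in both arms, and routine self-monitoring is required only in run-in and treatment. Step 3 shows that this period barely moves the difference.
- Each subject counts once per event type, so a longer window cannot lower the active count. The contrast shrinks only if placebo gains relatively more cases.
- Heavy placebo rescue is not supported by anything in the plan. Entry requires HbA1c of 8.5% or less, and stopping needs a confirmed fasting value of at least 270 mg/dL. At the top of the step 5 range, 0.40 × 12 + 0.16 × 24 = 8.6 subjects would be rescued, against 36 − 30 = 6 expected non-completers for any reason (although rescued patients who stay might count as completers).
- In the central case of step 5, the shift of 12 − 7.3 = 4.7 points is smaller than the standard error of the difference: √(0.15 × 0.85/24 + 0.03 × 0.97/12) = 8.8 points.
- Counting all events by assigned arm is a defensible policy. An on-drug table using crude percentages has its own bias, because it cuts observation time in whichever arm is rescued more.
- The 8.2.3 sentence leaves the call to the investigator and may be a slip of wording.
- Section 8 defers detail to a statistical analysis plan. No TEAE end date appears in the supplied text, so that plan is a natural place to set one.

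**Conclusion.** The gap is real and worth closing before unblinding. The TEAE window has no end tied to last dose, and post-drug and post-rescue events are pooled with on-drug events under the assigned arm. The expected effect is dilution of the primary safety comparison. With about 12 placebo subjects, one or two such events could move it materially in either direction. The size cannot be fixed from the documents: they give no hypoglycaemia rate and no rescue rate, and they name no rescue drug.

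A reader might go further and infer that the open window hides an excess of hypoglycaemia on the drug. The documents do not support that. It needs frequent rescue concentrated on placebo and a rescue drug with a high hypoglycaemia risk, both of which are assumed. In each of the two 3 × 3 sets of assumptions behind steps 4 and 5, only one combination of nine reverses the sign. Nor is the window unlimited, since collection stops at Visit 9. The 28-day follow-up of completers is not itself a masking mechanism.

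The 8.2.3 inconsistency needs no assumption. It follows from the order of procedures.

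**What to change.** 1. **Keep** the all-events-to-Visit-9 TEAE table.
2. **Add in 8.2.1 or the SAP** a display of hypoglycaemia and of all TEAEs by arm, in two periods:
   - on study drug: first randomized dose to last dose plus a fixed lag stated in the SAP, and before any rescue medication;
   - post-drug or post-rescue: from then to Visit 9.

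   For this purpose rescue should mean the medication offered after confirmed high glucose, because Section 3.7 also uses the word for glucose given after low values.
3. **Report subject-time at risk and exposure-adjusted rates** in each period. Crude percentages would mislead. If, for illustration, 3 of 12 placebo subjects stop at Day 28 and the rest complete, placebo on-drug time to Day 84 is 9 × 84 + 3 × 28 = 840 subject-days, against 12 × 84 = 1,008 (83%).
4. **In 8.2.3**, replace the TEAE wording with: *recorded as an AE and classified by onset date under 8.2.1*.

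The cost is SAP text and one extra table set. Dosing, IMP discontinuation and concomitant medication are already recorded (Sections 5.6, 7.5.1 and 6.6). Section 7.9 already anchors one rule, SAE follow-up, to the last dose. No clinical procedure changes.

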
Summary of Assessments
	
Safety Assessments: Safety will be assessed by monitoring adverse events including hypoglycemia, physical exam, vital signs (blood pressure (SBP/DBP), heart rate and oral temperature), ECG and clinical laboratory assessments.
 
Efficacy Assessments: Efficacy will be assessed by measuring the final and baseline differences in fat content obtained from MRI-PDFFF results.

Duration of Participation
	
Screening Phase: up to 42 days prior to the Treatment Phase Placebo Run-in Phase: 2 weeks Treatment Phase: 12 weeks End-of-Study (EOS) Phase: 4 weeks after completion of the Treatment Phase

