### **2.3 Primary Endpoint**

- To evaluate safety of ORMD-0801 in patients with nonalcoholic steatohepatitis (NASH) and type 2 DM.

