### 7.3 Adverse Events of Special Interest

#### 7.3.1 Adverse Events of Hypoglycemia

The CTCAE (version 5.0) criteria for mild, moderate, and severe hypoglycemia based on blood glucose will be used, as shown below:

Mild: < 70 – 55 mg/dL (< 3.8 - 3.0 mmol/L)

Moderate: < 55 – 40 mg/dL (< 3.0 - 2.2 mmol/L)

Severe: < 40 – 30 mg/dL (< 2.2 - 1.7 mmol/L)

Life Threatening: < 30 mg/dL (< 1.7 mmol/L)

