## 7.5 Recording Adverse Events

All adverse events experienced during the trial, regardless of relationship to study medication, must be recorded on the Adverse Event eCRF from the time of patient consent until completion of patients End-of-Study Visit (Visit 9). All serious adverse events will be collected through Visit 9. The Investigator must continue to follow all non-serious events possibly related to the study medication and all serious adverse events until they resolve or until the Investigator assesses them in writing as chronic or stable.

Regardless of relationship to study medication, the event must be recorded on the Adverse Event eCRF. Adverse event documentation should include the following information:

- Standard medical terminology for the AE
- Description of adverse event
- Date and time of onset
- Date and time of resolution of the adverse event
- Whether or not the event is ongoing
- Severity of the event
- Relationship between the adverse event and the investigational product
- Description of any actions taken (e.g., medications, treatments)
- Outcome of the AE
- Whether or not the effect was serious and/or unanticipated

Whenever possible, a diagnosis should be given when signs and symptoms are due to common etiology (e.g., cough, runny nose, sneezing, sore throat, and head congestion should be reported as "upper respiratory infection"). For the purposes of this study, hypoglycemic events will be considered adverse events and should be recorded in source and eCRF records.

When a diagnosis is not available, each adverse event should be reported separately. For example, "nausea and vomiting" should be split into two separate events.

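### No by-arm episode count or exposure-adjusted rate is specified for hypoglycemia, so recurrent episodes show only in individual listings and not in the safety summary tables

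*Combined protocol and SAP*

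**What the plan says.** The primary endpoint (Section 2.3) is stated in general terms: "To evaluate safety of ORMD-0801 in patients with nonalcoholic steatohepatitis (NASH) and type 2 DM". The synopsis names hypoglycemia within it: "Safety will be assessed by monitoring adverse events including hypoglycemia". Section 7.3 has hypoglycemia as its only topic and grades it by glucose level in four bands: "The CTCAE (version 5.0) criteria for mild, moderate, and severe hypoglycemia based on blood glucose will be used". Section 7.5 adds that "hypoglycemic events will be considered adverse events and should be recorded in source and eCRF records".

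Section 8.2.1 sets the analysis for all treatment-emergent events: "The incidence for each TEAE will be provided as the total number of subjects that experienced the TEAE", together with the percentage. For repeats, "If a TEAE is reported more than once for a given subject, the greatest severity and the worst-case attribution will be presented"; the sentence goes on to limit this to the summary tables. The same section plans individual listings with onset and end dates, severity, action taken and outcome. It also plans separate summaries of serious events and of events leading to withdrawal, and it rules out inferential comparison of adverse events between arms.

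Section 8 does not mention hypoglycemia, the Section 7.3.1 bands or diary glucose by name. Its opening paragraph defers further detail to a statistical analysis plan.

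**The concern.** Hypoglycemia can recur, and the protocol treats recurrence as informative. Section 3.7 requires fasting self-monitoring three times a week, with extra readings when symptoms occur, and bases one discontinuation criterion on a count of low values. A count of subjects with a worst grade answers whether a subject was ever affected and how badly. It does not answer how often. Two arms can look alike on the first question and differ several-fold on the second. For an insulin product in a trial whose primary endpoint is safety, frequency by arm is something a reader of the safety tables will want.

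Time at risk is also unaddressed in these tables. Treatment-emergent status starts at the first dose at Visit 3 and has no stated end on drug. Adverse events are collected to Visit 9, and subjects taken off drug for glucose reasons continue to be seen. About 6 of 36 randomized subjects are expected not to complete.

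**Working it through.** The plan states no hypoglycemia rate, power or precision, so there is no figure of its own to reproduce. The event rates below are assumptions.

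**Inputs from the protocol.** 36 subjects randomized 2:1 (Sections 3.1 and 5.2): 36 × 2/3 = 24 active, 36 × 1/3 = 12 placebo. Treatment lasts 12 weeks (Section 3.4). Three scheduled fasting readings a week (Section 3.7).

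**Data collected against data summarized.**
- Scheduled readings per subject on treatment: 3 × 12 = 36.
- By arm: 24 × 36 = 864 active and 12 × 36 = 432 placebo, plus symptom-driven readings.
- Full exposure: 24 × 12 = 288 and 12 × 12 = 144 person-weeks.
- The per-subject table reduces hypoglycemia to at most 24 and 12 yes/no indicators, each with a worst grade.

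**Equal incidence, unequal frequency (assumed).**
- Affected subjects: 6/24 = 25% active and 3/12 = 25% placebo.
- One episode per affected subject in both arms: 6/288 = 0.021 and 3/144 = 0.021 per person-week, ratio 1.
- Four per affected active subject, one on placebo: 24/288 = 0.083 against 3/144 = 0.021 per person-week, ratio 4.
- The incidence row reads 25% against 25% in both cases.

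**Contrast lost when the true rate ratio is 2.** With m the mean episodes per subject over 12 weeks, the chance of at least one episode is 1 − exp(−m) under a Poisson model. With strong between-subject variation (negative binomial, dispersion 1) it is 1 − 1/(1 + m).

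| Mean episodes, placebo vs active | Poisson incidence | Ratio | Negative binomial incidence | Ratio |
|---|---|---|---|---|
| 0.25 vs 0.5 | 22% vs 39% | 1.78 | 20% vs 33% | 1.67 |
| 1 vs 2 | 63% vs 86% | 1.37 | 50% vs 67% | 1.33 |
| 3 vs 6 | 95% vs 99.8% | 1.05 | 75% vs 86% | 1.14 |

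At low rates the subject count keeps most of the contrast. At high rates it loses nearly all of it.

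**Episodes not reflected in a subject count.** The share is 1 − P/m, with P = 1 − (1 + m/k)^(−k). Over an assumed range of m from 0.25 to 4 and k from 0.5 to 2:
- m = 0.25, k = 2: P = 0.210, share 1 − 0.210/0.25 = 16%.
- m = 1, k = 1: P = 0.500, share 50% (24 active episodes appear as 12 subjects).
- m = 4, k = 0.5: P = 0.667, share 1 − 0.667/4 = 83%.

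**Severity scales side by side.** Section 7.3.1 grades hypoglycemia by CTCAE version 5.0 in four glucose bands. Section 7.7 gives a three-level scale based on effect on daily activity. Section 8.2.1 says "The severity of AEs will be graded according to NCI CTCAE version 4.03". The worst grade shown per subject depends on which of these applies.

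**The case against.** The strongest reply is that nothing is lost. The worst-case rule covers only what "the greatest severity and the worst-case attribution will be presented in the summary tables" describes. Dated individual listings are planned, Section 8.2.7 promises descriptive statistics and listings for all data, and Section 8.2.2 plans by-visit summaries and shift tables for laboratory values, which include glucose. With about 36 subjects, repeats can be counted by hand. A reader might infer that the generic rule is the only analysis stated, or that recurrences are hidden altogether; the documents support neither. What stands is that listings give no summary by arm, and counting from them after unblinding would need an episode rule devised at that point.

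A reader might also infer that stopping because of hypoglycemia lowers the apparent risk. It does not: that subject has already had the event and is already counted, and withdrawals due to adverse events are summarized separately. Only stopping before any event could lower per-subject incidence.

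Three further limits hold. The primary endpoint is safety as a whole, so hypoglycemia is a component of it and not a defined primary variable. The statistical analysis plan to which Section 8 defers may already contain a rate; no separate text of it is among the documents reviewed. And a modelled rate ratio with a confidence interval by glucose band would be unstable with about 24 and 12 subjects, and would sit poorly with the statement in Section 8.2.1 that no inferential comparison is planned.

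**Conclusion.** The point holds in a limited form. The text available specifies no episode count or exposure-adjusted rate by arm for the one adverse event of special interest, so recurrence is visible only in individual listings. Equal incidence in the tables is compatible with a several-fold difference in frequency, as the assumed 25% vs 25% example with a rate ratio of 4 shows.

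The practical loss cannot be fixed from the documents, because they give no event rate. For a true doubling under the Poisson assumption, the incidence ratio runs from 1.78 at 0.25 vs 0.5 episodes per subject to 1.05 at 3 vs 6. If hypoglycemia is rare in this trial, the planned table serves nearly as well as a rate. This is a cheap improvement to the reporting of a central safety question, and not a flaw that invalidates the safety analysis.

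**What to change.** In Section 8.2.1, or in the statistical analysis plan to which Section 8 refers:

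- Keep the per-subject table. Add one descriptive table by arm and Section 7.3.1 glucose band with subjects affected, number of episodes, and crude episodes per person-week on study drug.
- Define time on drug (for example, first dose at Visit 3 to last dose) and fix the episode-counting rule before unblinding; the 10-minute rechecks in Section 3.7 should belong to one episode.
- Report by arm the proportion of scheduled fasting diary readings below 70 mg/dL. Exclude symptom-triggered readings and rechecks, which would otherwise over-represent low values.
- Reconcile the severity scales in Sections 7.3.1, 7.7 and 8.2.1, and state which one determines the worst grade shown.

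No model-based rate ratio is needed. The cost is one extra table, one diary summary line and a counting rule. Diary glucose values and hypoglycemic events already go to the eCRF (Sections 3.7 and 7.5), so no new assessments are required, provided that scheduled readings can be told apart from symptom-triggered ones in the database.
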